7.1 Required Medications

7.1.1 Prednisone

7.1.1.1 Product Description

Prednisone tablets will be purchased and over-encapsulated by DAIT NIAID's Clinical Product Center under contract, EMINENT Services Corporation (EMINENT), for the conduct of Protocol AIG01. The over-encapsulation is for the purpose of patient's safety and regimen adherence.

7.1.1.2 Formulation, Packaging, and Labeling

EMINENT will over-encapsulate, bottle, label, package and distribute prednisone tablets to the clinical site's investigational pharmacies. The details for the prednisone bottles are as follows:

DOSE	Directions	# of Capsules
40mg	1 pill daily for 2 weeks	30
30mg	1 pill daily for 2 weeks	30
20mg	1 pill daily for 1 week	12
15mg	1 pill daily for 1 week	12
10mg	1 pill daily for 1 week	12
7.5mg	1 pill daily for 1 week	12
5mg	1 pill daily for 1 week	12
2.5mg	1 pill daily for 1 week	12

7.1.1.3 Dosage and Administration

Participants in Part 1 and Part 2 will begin dosing with prednisone on the day of their first elotuzumab/placebo infusion. The ten-week dosing taper is described below:

Study Day	Prednisone Dose
Day 0 to Day 13	40 mg/day for two weeks, then
Day 14 to Day 27	30 mg/day for two weeks, then
Day 28 to Day 34	20 mg/day for one week, then
Day 35 to Day 41	15 mg/day for one week, then
Day 42 to Day 48	10 mg/day for one week, then
Day 49 to Day 55	7.5 mg/day for one week, then
Day 56 to Day 62	5 mg/day for one week, then
Day 63 to Day 69	2.5 mg/day for one week, then Discontinue

Based on the investigator's judgement, participants who present with aggressive disease or who require a higher starting dose of prednisone because of a large body mass index may be placed on up to 60 mg prednisone daily during the screening period. The dose will need to be decreased to 40 mg prednisone /day by the baseline visit. Participants who have been on prednisone 40 mg/day for at least two weeks during the screening period will begin Day 0 on 30 mg/day of prednisone and stay on 30 mg/day to Week 4 before continuing to taper prednisone from Week 5 onwards according to the schedule described above.

Participants on less than 40 mg/day for two weeks during the screening period will begin the prednisone taper from Day 0, beginning with 40 mg/day.

It is anticipated that in some participants, an interruption of the protocol-specified prednisone taper may be required (e.g., in the setting of an infection). This will be handled as follows:

- If the participant's protocol-specified prednisone taper is modified in the setting of infection, the protocol-specified prednisone taper will resume at the dose the participant was taking at the time of modification, once medically appropriate.

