6.3 Assessment of Participant Dosing Compliance

Elotuzumab/placebo will be administered intravenously at sites by trained medical staff. Compliance, therefore, will be monitored by the site and documented on the electronic Case Report Form (eCRF).

Dosing compliance with oral prednisone (see Protocol Section 7.1.1.3) will be assessed by pill count at each visit. Study personnel will calculate compliance in the presence of the participant so that reinforcement/re-education can be conducted as needed. Drug accountability and compliance will be documented on the source visit record and in the electronic data capture system.

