8.1 Visit Windows

Appendix 1 presents the Schedule of Events Tables for Part 1 and Part 2. The date for all visits are calculated relative to the date of the Baseline/Day 0 Visit. The visit windows are defined below:

Part 1A:

- Screening until Baseline/Day 0: 28 days from time of obtaining informed consent until randomization and initiation of study treatment
- Weekly infusion visits*: + 3 days / - 1 day
- Every 2-week infusion visits: \pm 3 days

Monthly follow-up visits: \pm 5 days

* Weekly infusion visits must be scheduled to allow for a minimum of four full days between infusions.

Part 1B and 2:

- Screening until Baseline/Day 0: 28 days from time of obtaining informed consent until randomization and initiation of study treatment
- Day 7: \pm 2 days
- Safety Visits (Weeks 4, 12, 20, 28, 36, 44, 48): \pm 7 days
- Infusion Visits (Weeks 8, 16, 24, 32, 40): \pm 7 days

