Plasma Collection		X	X	X			X				X	X	X	X
Submandibular Gland Biopsy ¹⁰		X								X ^{10a}	X ^{10a}			
Study Drug Administration														
EVUSHIELD/COVID-19 Prophylaxis ¹⁸	X													
Elotuzumab 10 mg/kg IV		X		X	X	X								
Oral steroid		X		X	X	X	X	X						
Steroid compliance check and dispensing				X	X	X	X	X						

¹ Baseline and Day 0 assessments may be split to accommodate salivary gland biopsy so long as first infusion occurs within 28 days of start of screening.

² Height at screening. The screening weight may be used for calculation of all doses as long as there is a less than 10% change over the study treatment period (or as consistent with institutional policy).

³ Imaging required to complete a full IgG4-RD RI assessment will be performed for the Screening visit. Specifically, all participants will undergo either a CT or MRI of the chest, abdomen, and pelvis at Screening. Participants with clinical evidence of orbital disease will also undergo CT or MRI of that area. If abnormalities in a particular area are detected at Screening, the participant will have the same type of study repeated at Week 24. Imaging at week 24 will be performed if there is a clinical reason to suspect disease activity at that site. Imaging may also be repeated at the discretion of the investigator at a visit other than those two time points if required to assess disease activity because of a potential disease flare or to assess an adverse event.

^{3a} Oral or intravenous contrast agents may be used in some radiology studies. The need for contrast agents will be reviewed on an individual basis, consistent with the routine use of these imaging studies. Consultation with radiology will be obtained as needed.

⁴ eGFR to be calculated centrally per the CKD-EPI formula.

⁵ ELF Score serology: TIMP-1, PIIINP, HA.

⁶ By Interferon-Gamma Release Assay (IGRA). If indeterminate, repeat (with same or other IGRA per local policy) or obtain PPD (the latter to be read within 48-72 hours and may be read locally with documentation of result by health care provider). If history of BCG vaccine or other complication in interpretation of result, consultation with ID is required for clearance to proceed.

⁷ HIV, Hepatitis B surface antigen and Hepatitis B core antibody, Hepatitis C antibody.

⁸ U/A macroscopic and microscopic analysis, culture if indicated.

⁹ For women of child-bearing potential. Stat urine HCG prior to each infusion may be performed locally with point of care testing.

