Adverse Event Assessment		X	X	X	X	X	X	X	X	X	X	X	X	X	X	X
Concomitant Medications	X	X	X	X	X	X	X	X	X	X	X	X	X	X	X	X
SARS-CoV-2 Antigen Test ¹⁷		X			X		X		X		X		X			
Disease Activity Assessments																
CT scan w/ or MRI w/o contrast ^{3, 3a}	X														X	X
IgG4-RD Responder Index (RI) ¹³	X	X ¹⁶													X	X
Physician Global Assessment VAS	X	X		X	X	X	X	X	X	X	X	X	X	X	X	X
Patient Global Assessment VAS	X	X		X	X	X	X	X	X	X	X	X	X	X	X	X
Flare Documentation Guide ¹²	X	X		X	X	X	X	X	X	X	X	X	X	X	X	X
SF-36 Health Survey		X			X		X		X		X		X		X	X
Clinical Laboratory Assessments																
CBC with differential/ANC ^{11, 11a}	X	X		X	X	X	X	X	X	X	X	X	X	X	X	X
Comprehensive Metabolic Panel ^{11, 11a}	X	X		X	X	X	X	X	X	X	X	X	X	X	X	X
Serum amylase and lipase	X	X		X	X	X	X	X	X	X	X	X	X	X	X	X
eGFR ⁴	X	X		X	X	X	X	X	X	X	X	X	X	X	X	X
Serum Immunoglobulins ¹⁵		X			X		X		X		X		X		X	X
Serum IgG subclasses		X			X		X		X		X		X		X	X
ESR		X			X		X		X		X		X		X	X
CRP		X			X		X		X		X		X		X	X
Serum complement: C3 and C4		X			X		X		X		X		X		X	X

Visit Name	Screening	Base-line/ Day 0 ¹	Day 7 (phone call)	Week 4	Week 8	Week 12	Week 16	Week 20	Week 24	Week 28	Week 32	Week 36	Week 40	Week 44	Week 48	Unscheduled ¹⁴
Visit window	-28 days	N/A	±2 days	±7 days	±7 days	±7 days	N/A									
ELF score ⁵		X			X			X		X			X			X
TB Testing ⁶	X															
Clinical Laboratory Assessments (continued)																
Other infectious disease testing ⁷	X															
Urinalysis and culture ⁸	X									X					X	X
Serum HCG ⁹	X															
Urine HCG ⁹		X			X		X		X		X		X			
Mechanistic Assessments																
Flow Cytometry: PBMC collection	X ¹⁸	X ¹⁸			X		X		X		X		X		X	X
Plasma Collection	X ¹⁸	X ¹⁸			X		X		X		X		X		X	X
Submandibular Gland Biopsy ¹⁰	X ¹⁹	X ¹⁹											X ^{10a}	X ^{10a}		
Study Drug Administration																
Elotuzumab/placebo 10 mg/kg IV		X			X		X		X		X		X			
Oral steroid		X		X	X											
Steroid compliance check			X	X	X	X										

¹ Baseline/Day 0 assessments may be split to accommodate submandibular gland biopsy so long as first infusion occurs within 28 days of start of screening.

² Height at screening. At the Baseline/Day 0 visit, the screening weight will be used for calculation of the baseline infusion dose. For all subsequent infusions, the weight assessed at the previous infusion visit will be used for calculation of dose.

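### Minor: the 30 mg prednisone bottle carries only a two-week direction, but participants who start at 30 mg must take that dose for four weeks

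*Combined protocol and SAP*

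**What the plan says.** Section 7.1.1.3 (Dosage and Administration) sets out a taper from Day 0 to Day 69. The standard track takes 40 mg on Days 0 to 13, 30 mg on Days 14 to 27, and then six one-week steps from 20 mg on Day 28 down to 2.5 mg. Participants already on 40 mg/day for two weeks or more in screening begin on 30 mg instead and "stay on 30 mg/day to Week 4 before continuing to taper prednisone from Week 5 onwards according to the schedule described above". Section 3.1.3 gives both starts the same ten-week taper. Section 6.1.4 names 7.1.1.3 as the place where the oral steroid regimen is described for everyone in both parts.

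Section 7.1.1.2 (Formulation, Packaging, and Labeling) lists the bottles by strength. The 30 mg bottle appears once, with 30 capsules and the direction "1 pill daily for 2 weeks". No other 30 mg bottle or direction is given. Section 7.1.1.1 explains the capsules: "The over-encapsulation is for the purpose of patient's safety and regimen adherence".

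Section 6.3 has pill counts at each visit, done with the participant present, "so that reinforcement/re-education can be conducted as needed". In the Appendix 1 schedule for Parts 1B and 2, the row "Steroid compliance check" is marked at the Day 7 phone call and at Weeks 4, 8 and 12.

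**The concern.** The two adjacent sections disagree for one of the two permitted starts. A participant who begins on 30 mg and does what the bottle table says leaves that dose after two weeks, when the regimen requires four. Prednisone is required background treatment in both arms, and the protocol gives safety and adherence as the purpose of the capsules. A dosing direction that is wrong for a group the protocol plans for works against that purpose. At stake is a taper up to two weeks too short in that group, and avoidable protocol deviations. The documents do not say how many participants will start at 30 mg.

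**Working it through.** **Inputs.** Doses and days: table in 7.1.1.3. Bottle direction and capsule count: 7.1.1.2. Ten-week length for both starts: 3.1.3. Week 4 visit window of plus or minus 7 days, so Day 21 to Day 35: 8.1.

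**1. The plan's own length.** Standard track: 14 + 14 + 6 × 7 = 70 days, Day 0 to Day 69, which reproduces the stated ten weeks. The six lower steps total 7 × (20 + 15 + 10 + 7.5 + 5 + 2.5) = 7 × 60 = 420 mg. Full total: 14 × 40 + 14 × 30 + 420 = 560 + 420 + 420 = 1400 mg.

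**2. What a 30 mg starter needs.** The six lower steps take 42 days and begin on Day 28. That leaves 70 − 42 = 28 days at 30 mg, Days 0 to 27. Total: 28 × 30 + 420 = 840 + 420 = 1260 mg.

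**3. What the bottle directions give if followed to the end.** This assumes that the next bottles are in hand on Day 14.

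| | Required (30 mg start) | Bottle directions followed |
|---|---|---|
| Days at 30 mg | 28 | 14 |
| Length | 70 days | 14 + 42 = 56 days |
| Last dose | Day 69 | Day 55 |
| Total | 1260 mg | 14 × 30 + 420 = 840 mg |

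The shortfall is 1260 − 840 = 420 mg, and 840/1260 = 66.7%.

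**4. Supply.** 30 capsules − 28 needed = 2 spare. The bottle is large enough; only the direction is wrong.

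**5. If it is caught at the Week 4 visit.** This assumes step 3 up to that day and the correct table dose from that day on.

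- Day 21: 420 + 140 + 7 × 30 + 420 = 1190 mg (94.4% of 1260).
- Day 28: 420 + 140 + 105 + 420 = 1085 mg (86.1%).
- Day 35: 420 + 140 + 105 + 70 + 7 × (15 + 10 + 7.5 + 5 + 2.5) = 1015 mg (80.6%).

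If the Day 7 call corrects it, nothing is lost.

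**6. The step-3 course with screening added.** Taking exactly two weeks at 40 mg in screening, the doses are 14 × 40 + 14 × 30 + 420 = 1400 mg over 70 days. That is the standard sequence of step 1, begun two weeks before Day 0.

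**The case against.** The strongest reply is that 7.1.1.2 is a packaging table written for the standard track, and that 7.1.1.3, the section the protocol names as the regimen, is explicit for the 30 mg start. Site staff who read it will tell the participant four weeks. The printed label, the pharmacy manual and any dosing calendar are not in the file, so we cannot say that a participant would receive an uncorrected direction. This largely stands. It limits the consequence, but it leaves 7.1.1.2 wrong for a permitted start.

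The timing of dispensing is also open. The Part 1A schedule has a row "Steroid compliance check and dispensing"; the row for Parts 1B and 2 drops the dispensing. There the oral steroid row is marked at Baseline, Week 4 and Week 8. If those are the hand-out dates, a participant on Day 14 holds 16 capsules of the correct strength and no lower ones, and the early step-down in steps 3 and 5 does not arise.

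The harm is modest too. Step 6 shows that even the full error yields the standard steroid course, only earlier. It departs from the protocol's timing but is not an abnormal taper.

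A reader might go further and infer three things that the documents do not support:

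- **A biased or weakened primary comparison.** Both arms follow the same prednisone directions under blinding, and nothing in the file links this shortfall to flares or to the Week 48 response.
- **Too few capsules.** Step 4 rules this out.
- **Loss from the per-protocol population.** The full error would fall below the 80% floor in 13.4.1, but that requires every check to fail. Caught at Week 4, all three totals stay above 0.80 × 1260 = 1008 mg. This takes the participant's own track as the base, which 13.4.1 does not spell out; against 1400 mg, the Day 28 and Day 35 totals would be 77.5% and 72.5%. Either way, the primary analysis uses the mITT population.

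**Conclusion.** The point holds as a minor drafting error. The direction in 7.1.1.2 covers 14 of the 28 days that a 30 mg starter must spend on that dose. That conclusion needs no assumption beyond the protocol's own table and ten-week length.

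The dosing consequence is conditional. Its upper end, 420 mg short with the last dose 14 days early, requires an unaltered label, lower strengths in hand by Day 14, and no correction at baseline, on the Day 7 call or at the Week 4 pill count. Baseline instruction is ordinary practice and is not described in the file; the other two checks are scheduled. An error that lasts the whole taper is therefore unlikely, and the realistic range runs from no loss to the partial shortfalls of step 5. The number of participants exposed is unknown.

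**What to change.** In 7.1.1.2 and on the bottle label, add a separate 30 mg direction for participants who start at 30 mg: one pill daily for 4 weeks (Days 0 to 27). Keep the present two-week direction for the 40 mg start. If the pharmacy manual already does this, 7.1.1.2 should be brought into line with it.

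The cost is one line of protocol text and a second label version for one bottle. No extra capsules, visits, procedures or participants are needed, and the analysis does not change.

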7.2 Standard of Care Recommended/Permitted Therapies

- Course of glucocorticoids for non-IgG4-RD indications that are discontinued within 2 weeks: only 2 such courses are permitted and must be complete by 8 weeks prior to the Week 48 visit.
- Potential participants are encouraged to obtain vaccines as standard of care per age-specific Center for Disease Control and Prevention (CDC) guidelines before participating in the study. Live vaccines must be avoided within 8 weeks of initiation of study drug. If possible it is suggested participants obtain other immunizations at least 4 weeks prior to initiation of study therapy. Seasonal flu vaccine should be obtained during the course of the study. Other non-live vaccines as needed for standard of care may be administered.
- Concomitant therapies taken for the long term treatment of pre-existing conditions other than IgG4-RD may be continued during the study provided they are in accordance with the exclusion criteria and the list of prohibited medications. During the study, concomitant medications and new medications should be administered at the discretion of the site investigator or treating physician in order to provide the participant with the best possible medical care.
- Medications used for prevention and treatment of COVID-19, approved by the FDA or authorized for emergency use, are permitted.
- Participants should continue to receive SARS-CoV-2 vaccinations per CDC and FDA recommendations and other seasonal vaccinations during the course of the study.

7.3 Prohibited Medications

All participants are to have access to any care deemed medically necessary, but administering the following medications, for the purposes of this study, are prohibited and will be considered protocol deviations unless administered for a disease flare:

- Any systemic glucocorticoids, except for:
 - Prednisone (or equivalent) detailed in Section 7.1.1: Prednisone and in 7.2: Standard of Care Recommended/Permitted Therapies
- Any biologic or non-biologic immunomodulating drug therapy including but not limited to methotrexate, mycophenolate mofetil, 6-mercaptopurine, tacrolimus, cyclophosphamide, azathioprine, rituximab or other CD20 depleting agents.
- Investigational agents or treatments are prohibited during study participation, except for SARS-CoV-2 vaccines as specified in Section 6.4.2.3.
- Live vaccines within 8 weeks prior to initiation of study therapy and during study participation.

8 Study Procedures

8.1 Visit Windows

Appendix 1 presents the Schedule of Events Tables for Part 1 and Part 2. The date for all visits are calculated relative to the date of the Baseline/Day 0 Visit. The visit windows are defined below:

Part 1A:

- Screening until Baseline/Day 0: 28 days from time of obtaining informed consent until randomization and initiation of study treatment
- Weekly infusion visits*: + 3 days / - 1 day
- Every 2-week infusion visits: \pm 3 days

Monthly follow-up visits: \pm 5 days

* Weekly infusion visits must be scheduled to allow for a minimum of four full days between infusions.

Part 1B and 2:

- Screening until Baseline/Day 0: 28 days from time of obtaining informed consent until randomization and initiation of study treatment
- Day 7: \pm 2 days
- Safety Visits (Weeks 4, 12, 20, 28, 36, 44, 48): \pm 7 days
- Infusion Visits (Weeks 8, 16, 24, 32, 40): \pm 7 days

8.2 Unscheduled Visits

Unscheduled visits may be performed if disease activity increases or for other concerns between regularly scheduled visits. In the event of a disease flare, the assessments and procedures outlined for the Week 24 visit should be obtained. For unscheduled visits conducted for a reason other than a disease flare, participants should be evaluated per clinical judgement of the investigator.

8.3 Screening and Enrollment

This study will be explained in lay language to each potential participant. Each participant will sign an informed consent form before committing to study screening procedures.

After obtaining informed consent, all screening assessments and procedures to establish eligibility will be performed. These may be completed during one or more study visits within the 28-day screening window.

The following labs, procedures, and assessments will determine participant eligibility:

8.3.1 Evaluation of Eligibility and Randomization

In Part 1, if the participant meets all eligibility criteria for enrollment, then proceed as follows:

- Schedule Baseline/Day 0 Visit (within 28 days of 1st Screening assessment)

In Part 2, if the participant meets all eligibility criteria for enrollment, then proceed as follows:

- Schedule Baseline/Day 0 Visit (within 28 days of 1st Screening assessment)
- Randomize the participant

Randomization will be accomplished through a password-protected, web-based, randomization system maintained by the Statistical and Clinical Coordinating Center (SCCC).

8.4 General Assessments

See Schedule of Events Tables in Appendix 1: **Schedule of Visits and Assessments** for more detailed information.

- Demographics
- Medical History
- Comprehensive physical examination: to include an evaluation of the head, ears, eyes, nose, throat, lymph nodes, heart, lungs, abdomen, skin, extremities, and neurology.
- Targeted physical examination: to include heart, lungs, and abdomen. Additional evaluations to be guided by participant complaints and prior abnormalities.
- Vital Signs
- Weight/Height
- Adverse Events
- Concomitant medications: Any medication related to IgG4-RD taken at any point should be recorded. Other non-IgG4-RD related concomitant medications taken 30 days prior to screening through study completion or termination should be reported.
- SARS-CoV-2 Antigen Testing: Participants must be confirmed negative for SARS-CoV-2 by antigen test within 24 hours of infusion. Participants are provided antigen tests by the site, test themselves, and provide proof of negativity. Participants will otherwise will be monitored for SARS-CoV-2 according to institutional standards.

8.5 Clinical Laboratory Assessments

- Complete Blood Count (CBC) with diff, ANC
- Comprehensive Metabolic Panel: to include total protein, potassium, sodium, calcium, chloride, albumin, glucose, blood urea nitrogen (BUN), creatinine, total bilirubin, direct bilirubin, alkaline phosphatase , aspartate aminotransferase (AST), alanine aminotransferase (ALT).
- Serum amylase and lipase
- eGFR (calculated centrally based on the Chronic Kidney Disease Epidemiology (CKD-EPI) formula [40]).
- Serum Immunoglobulins
- Serum IgG subclasses
- IgE
- Erythrocyte Sedimentation Rate (ESR)
- C-reactive protein (CRP)
- Serum complement levels: C3 and C4
- TB Testing: IGRA
- Other Infectious Disease Testing: HIV, Hepatitis B surface antigen and core antibody, Hepatitis C antibody test
- Urinalysis: macro, microscopic, culture as indicated
- Serum human chorionic gonadotropin (HCG) (women of child-bearing potential)
- Urine HCG (women of child-bearing potential): pre-infusions

8.6 Disease-Specific Assessments

- ACR Classification Criteria
- IgG4 History, including all assessments of serum IgG4 concentration obtained within 6 months of the Baseline visit.
- CT scan or MRI: chest, abdomen, pelvis. Include head and/or orbits if head/neck/intraocular muscle involvement
- IgG4-RD Responder Index
- Physician Global Assessment VAS

- Patient Global Assessment VAS
- SF-36 Health Survey
- Flare Assessment

9 Mechanistic Assays

During Part 1A, PBMCs and plasma will be isolated and frozen from each participant at baseline and then two days after the first elotuzumab infusion. Subsequent samples will also be obtained at 1, 5, 16, 24, and 48 weeks, with corresponding clinical blood draws. During Part 1B and 2, samples will be collected at Screening or Baseline/Day 0 and Weeks 8, 16, 24, 32, 40 and 48, corresponding with clinical blood draws. Samples should not be collected at Screening if the participant is taking glucocorticoids on the day of the Screening Visit. If samples were not collected at the Screening Visit, they must be collected at Baseline/Day 0. Mechanistic samples will be obtained on all participants at all sites at the specified timepoints. PBMCs and plasma will be stored in liquid nitrogen for preservation. The mechanistic studies will be conducted at both the Massachusetts General Hospital/Ragon Institute and Emory University. Further instructions to the site on shipment of biospecimen will be provided in the Lab Manual. The following experiments will be carried out in batches of 10 participant timepoints per experiment:

- Flow cytometric quantification of plasmablasts, activated B cells, terminally differentiated CD4+CTLs, terminally differentiated CD8+CTLs, activated TFH cells, and TPH cells. Terminal differentiation will be defined by the loss of CD28 surface expression and gain of CD57 surface expression within the respective effector (CD45RA-CCR7-) T cell population. These cell populations will be assessed on the schedule noted above to determine the treatment effect on the absolute numbers and proportions of these cell types.
- Quantified cell populations will be analyzed for correlation with one another, disease activity, plasma IgG4 levels and clinical responsiveness to elotuzumab.
- From 5 of the enrolled participants with known expansions of the respective cell type and clinical responsiveness to elotuzumab, terminally differentiated CD4+CTLs, terminally differentiated CD8+CTLs, and activated B cells will be sorted by FACS at weeks 0, 16, 24, and 48. RNA will be isolated to undergo RT-PCR amplification of the TCR- β /IgH. Next-Generation Sequencing will be used to define the diversity of the TCR/BCR repertoire longitudinally to ascertain how elotuzumab may impact clonality.

